7. RISKS/PRECAUTIONS

7.1 Risks

In clinical studies, IV difelikefalin has been administered to 1,096 CKD subjects on HD for at least 12 weeks (3 months); of these subjects, 415 CKD subjects on HD with moderate-to-severe pruritus have been exposed to IV difelikefalin for at least 48 weeks (12 months).

The most common ($\geq 5.0\%$ of subjects) AEs reported from clinical studies with IV difelikefalin in subjects with CKD on HD with an incidence $\geq 1.0\%$ greater compared with placebo were, in descending frequency, diarrhoea, nausea, fall, hypotension, dizziness, vomiting, abdominal pain, hyperkalaemia, headache, pneumonia, dyspnoea, constipation, somnolence, pyrexia, and blood thyroid stimulating hormone decreased.

Risk of Driving and Operating Machinery

Dizziness, somnolence, and mental status changes have occurred in subjects taking IV difelikefalin. IV difelikefalin may impair the mental or physical abilities needed to perform potentially hazardous activities, such as driving a car and operating machinery. Subjects should be advised not to drive or operate dangerous machinery until the effect of IV difelikefalin on a subject's ability to drive or operate machinery is known.

Dizziness, Somnolence, Mental Status Changes, and Gait Disturbances

Dizziness, somnolence, mental status changes, and gait disturbances, including falls, have occurred in subjects taking IV difelikefalin and may subside over time with continued treatment.

Somnolence (including MedDRA PTs of somnolence and sedation) and mental status changes (including MedDRA PTs of mental status changes and confusional state) have been reported as serious ADRs, with frequencies of 0.12% and 0.17%, respectively, in subjects being treated with difelikefalin during clinical developmental (including the indication for treating pruritus; N=3,478).

The incidence of somnolence was higher in IV difelikefalin-treated subjects (in the Phase3 studies) ≥ 65 years of age (7.0%) than in IV difelikefalin-treated subjects < 65 years of age (2.8%). Concomitant use of centrally acting depressant medications, sedating antihistamines, and opioid analgesics may increase the likelihood of these adverse reactions and should be used with caution during treatment with IV difelikefalin.

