10.8.4 Adverse Events of Special Interest

10.8.4.1 Definition of AESIs

An AESI is a medical occurrence specific to the product or program, for which ongoing monitoring and rapid communication by the Investigator to the Sponsor is appropriate. Such an event, depending on the nature and the outcome, may be serious (see Section 10.7.1) or non-serious.

Based upon results of the studies in the HD population, the following categories (MedDRA PT) were identified as AESIs for the HD population:

- Gait disturbance (gait disturbance)
- Falls (fall)
- Dizziness (dizziness)
- Somnolence (somnolence)
- Seizures (seizure)
- Syncope (syncope)
- Mental status changes (mental status changes)
- Mood changes (mood altered)
- Unusual feeling/sensation (feeling abnormal)
- Tachycardia (sinus tachycardia, tachycardia, and tachyarrhythmia)
- Palpitations (palpitations)

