12.3 Randomisation

All subjects enrolled must be identifiable throughout the study.

Randomisation of subjects will be performed on Day 1 before start of treatment with study drug.

Each eligible subject will be randomised during the double-blind period in a 1:1 allocation ratio to receive either difelikefalin or matching placebo using a validated centralised procedure (IWRS) that automates the random assignment of treatment groups to randomisation numbers. Subjects will be stratified according to their use or non-use of concomitant medications to treat their itch (refer to Section 6.8.1) during the week prior to randomisation (run-in period) as well as the presence or absence of specific medical conditions. These specific medical conditions include:

- History of fall or fracture (related to fall)
- Confusional state or mental status change or altered mental status or disorientation
- Gait disturbance or movement disorder

Randomised subjects who terminate their study participation for any reason regardless of whether the investigational product was taken or not, will retain their randomisation number. The next subject will be given the next randomisation number.

Before the start of the study, a randomisation list will be created for each stratum. The randomisation lists will be kept strictly confidential, accessible only to authorised persons, until the time of unblinding.

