4.8 Safety Analyses

All safety analyses are to be performed by treatment sequence and all sequences pooled using the OL-SAF and are to be descriptive. Missing values will not be imputed unless stated otherwise, please refer to [Section 4.1.9](#).

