4.8.1 Adverse Events

AEs data are collected from the time the informed consent form (ICF) is signed by the subject. The AE reporting period ends at the last study contact. Missing dates/partial dates of AEs will be handled as per [Section 4.1.9](#).

AEs relative to the open-label extension period are identified as any AE with an onset date on or after the first dose of difelikefalin in the open-label extension period.

All tabular adverse event summaries will only include AEs relative to the open-label extension period.

An AE will be classified as related to study drug if the relationship to study drug was recorded as 'Certain' or 'Probable/Likely' or 'Possible' in eCRF, as determined by the investigator. An AE will be classified as unrelated to study drug if the relationship to study drug was recorded as 'Unlikely' or 'Unrelated' in eCRF as determined by the investigator.

An SAE is defined as an AE when "Is this AE considered as Serious?" on the "Adverse Event" eCRF page is "Yes".

An AE leading to investigational product interruption is defined as an AE where the action taken with study drug is "Drug Interrupted" on the "Adverse Event" eCRF page. An AE leading to investigational product discontinuation is defined as is defined as an AE where the action taken with study drug is "Drug Withdrawn" on the "Adverse Event" eCRF page. An AE leading to early study termination is defined as an AE where other action taken is "Early Study Termination".

Adverse Events of Special Interest (AESI)

An AESI is a medical occurrence specific to the product or program. Any AE with the following MedDRA PT is to be identified as an AESI:

- gait disturbance
- fall
- dizziness
- somnolence
- seizure
- syncope
- mental status changes
- mood altered
- feeling abnormal
- sinus tachycardia, tachycardia, and tachyarrhythmia
- palpitations

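### Does the open-label SAP under-report sedation and confusional state by listing AESIs as single preferred terms?

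*SAP*

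**What the plan says.** SAP section 4.8.1 works from preferred terms: "Any AE with the following MedDRA PT is to be identified as an AESI". Somnolence and mental status changes are on the list; sedation and confusional state are not. AESI tables 14.3.1.10 and 14.3.1.11 in Appendix 1 are by preferred term. Section 4.8.1 counts a subject once within a system organ class or preferred term and has no level in between. SAP section 4.8 adds that safety analyses are done "using the OL-SAF and are to be descriptive".

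The list comes from Protocol section 10.8.4.1, which names a category and then, in brackets, the term or terms that make it up, for example "Mental status changes (mental status changes". It gives its basis as "Based upon results of the studies in the HD population".

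Protocol section 7.1, on risks, groups more broadly: "Somnolence (including MedDRA PTs of somnolence and sedation) and mental status changes (including MedDRA PTs of mental status changes and confusional state", closing the bracket there, "have been reported as serious ADRs, with frequencies of 0.12% and 0.17%, respectively, in subjects being treated with difelikefalin". The denominator is 3,478 subjects from the clinical programme, a population that is not confined to haemodialysis.

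**The concern.** The protocol seems to describe the same two central nervous risks in two ways: as pairs of terms in section 7.1, and as single terms in the AESI list. A subject whose drowsiness is coded as sedation, or whose mental change is coded as confusional state, is missing from the AESI tables. Adding up rows of the general tables does not repair this exactly, because a subject with both terms of a pair stands in two rows.

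The stratification factor in Protocol section 12.3 seems to support a wider grouping, since one of its items reads "Confusional state or mental status change or altered mental status or disorientation". If events of interest were lost, the extension would understate two recognised risks of the drug. The protocol gives the collection of more safety data as one purpose of the extension, so that would matter.

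**Working it through.** **1. SAP against protocol.** Compared line by line, the two AESI lists agree. Both have eleven categories, and only tachycardia has several terms (sinus tachycardia, tachycardia, tachyarrhythmia). The SAP neither narrows nor departs from the protocol.

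**2. Is there an inconsistency inside the protocol?** Section 10.8.4.1 defines AESIs and rests on haemodialysis studies. Section 7.1 is a risk statement that pools the programme. The haemodialysis term lists fit the narrower choice:
- Section 7.1 ends its list of common events with "constipation, somnolence, pyrexia, and blood thyroid stimulating hormone decreased", and sedation is nowhere in that list.
- Section 1.2.2.2 names somnolence and mental status changes in haemodialysis subjects, but neither omitted term. It names sedation only for healthy volunteers.

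**3. Are events lost?** Each planned output in SAP section 4.8.1 and Appendix 1 was checked for where an event coded to an omitted term would appear:

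| Output | Shows sedation and confusional state? |
|---|---|
| 14.3.1.2, all adverse events by organ class and term | Yes, each in its own row |
| 14.3.1.4, related events by organ class and term | Yes, if related |
| 14.3.1.5, related serious events by organ class and term | Yes, if serious and related |
| 14.3.2.1, listing of serious events | Yes, if serious |
| 16.2.7.1, by-subject listing of all events | Yes |
| 14.3.1.10, 14.3.1.11, 14.3.2.5, AESI outputs | No |

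Only the ready-made count of distinct subjects per pair is absent.

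**4. How uncertain is a grouped count from term rows alone?** With *a* subjects in one row and *b* in the other, the number of distinct subjects lies between max(*a*, *b*) and *a* + *b*. The documents give no open-label counts, so take *a* = 6 and *b* = 3 as an assumption. The count is then 6 to 9:
- 180 subjects (assumed): 6/180 = 3.3% to 9/180 = 5.0%.
- 200 subjects (assumed): 6/200 = 3.0% to 9/200 = 4.5%.
- 258 subjects (all randomised enter, the ceiling): 6/258 = 2.3% to 9/258 = 3.5%.

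The by-subject listing reduces each range to one exact figure.

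**5. The section 7.1 figures.** No numerators are given, so only consistency can be checked:
- 4/3,478 = 0.115%, which rounds to 0.12%.
- 6/3,478 = 0.173%, which rounds to 0.17%.
- No other whole number of subjects fits either percentage.

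If these rates carried over to 258 subjects, the expected numbers of serious related cases are:
- somnolence pair: 0.0012 × 258 = 0.31;
- mental status pair: 0.0017 × 258 = 0.44.

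Each figure covers both terms of its pair, so the part due to the omitted term is anywhere from zero to that value.

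**6. Other related figures.** The protocol also gives:
- Phase 3 somnolence incidence of 7.0% at age 65 or over and 2.8% below 65 (section 7.1);
- somnolence among events in at least 10% and at least 3% of subjects in the two Japanese Phase 2 haemodialysis studies (section 1.2.2.2);
- mental status changes among serious events in at least 1.0% of treated haemodialysis subjects (section 1.2.2.2). At 258 subjects that threshold is 0.01 × 258 = 2.6 cases, whatever the cause.

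None of these is stated to be a rate for an omitted term. A handful of serious cases can still be matched by subject in the listing.

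**The case for a change.** The best case for a change is that the sponsor itself thinks of these risks as pairs, already allows one AESI category several terms, and should not leave a reader to count subjects by hand. The factual part stands: no planned row unites either pair, and the organ class row and the overall AESI row cannot stand in for it.

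The rest is weaker:
- The tachycardia category cuts the other way. Where the protocol wanted several terms, it wrote them out.
- The stratification item describes conditions present before randomisation, not event coding. It also takes in altered mental status and disorientation, so it is not the section 7.1 pair.
- Section 7.1 states its grouping for serious reactions. A grouped table of all events, or of all related events, could not be set beside 0.12% and 0.17%. The like-for-like quantity is serious and related, which Table 14.3.1.5 and the listing of serious events already cover by term and by subject.
- The age-specific somnolence incidences do not say whether sedation is included, and SAP section 4.1.8 plans no subgroup analysis against which to read them.

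What remains is that a grouped table would save some hand counting.

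**Conclusion.** The concern does not hold. The SAP applies the protocol's AESI definition exactly, and that definition has its own stated basis in haemodialysis studies. Every event coded to sedation or confusional state is still tabulated and listed. No estimate, test or decision rule uses the grouped count, so following the plan as written leaves the safety conclusions sound.

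The size of what is left is unknown and may be zero. Each subject whose only event in a pair is the omitted term would move that pair's pooled incidence by 1/258 = 0.39 percentage points at the ceiling, or by 1/129 = 0.78 points within one treatment sequence. That subject is visible in the outputs either way.

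This rests on two assumptions: that events are coded and listed as the SAP describes, and that the section 7.1 rates are at least a rough guide for this population. The first carries the conclusion; the second bears only on the expected counts. It covers the extension only, because the double-blind period has a separate SAP that was not among the documents.

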4.8.2 Clinical Laboratory Evaluations

Subject clinical laboratory evaluations including serum chemistry, haematology and potassium will be summarized descriptively using central laboratory.

Laboratory values will be reported in units according to the International System of Units as per [Appendix 2](#) in the SAP.

Summaries of actual values and the change from baseline to each time point (when applicable) including last post-baseline measurement will be presented for quantitative laboratory parameters. Descriptive statistics are calculated by treatment sequence and all sequences pooled on both the actual values and the change from baseline.

Baseline is defined as the last measurement taken on or prior to the first day of open-label dosing. This will typically be the end of treatment visit for the double-blind period.

Laboratory test results will be classified according to whether the value was below (L), within (N), or above (H) the laboratory parameter reference range. A summary of shifts will compare the baseline L/N/H classification for each laboratory test to the L/N/H classification at end of open-label extension period and at last post-baseline. For serum potassium, shift table comparing the baseline L/N/H classification to each post baseline L/N/H classification (including last post-baseline) will also be provided.

All laboratory results will be listed, including data at any unscheduled visits. In addition, all abnormal (with classification of L or H) laboratory values will be presented in a separate listing.

4.8.3 12-lead Electrocardiogram (ECG) Evaluations

Summary tables for 12-lead ECG include descriptive statistics for baseline and each post baseline assessment including last post-baseline measurement during the open-label extension period. Descriptive statistics are calculated by treatment sequence and all sequences pooled on both the actual values and the change from baseline for Heart Rate, QT interval, QTcF interval, QTcB interval, RR interval, P-wave, QRS complex duration and PR interval. Overall interpretation of the 12-lead ECG readings is to be tabulated as well by treatment sequence and all sequences pooled at baseline, at end of open-label extension period and at last post-baseline assessment.

Baseline is defined as the last measurement taken on or prior to the first day of open-label dosing. This will typically be the end of treatment visit for the double-blind period.

All 12-lead ECG data will be listed in a by-subject listing and will be sorted by subject identifier and date of assessment.

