9.4 Clinical Laboratory Tests

The following clinical laboratory tests are to be performed via central laboratory as indicated in the Schedule of Events ([Table 1](#) and [Table 2](#)).

- Serum chemistry:
 - Albumin, bilirubin (total), AP, ALT, AST, glucose, creatinine, BUN
 - Electrolytes (sodium, potassium*, chloride, calcium, and phosphorus)
- Haematology:
 - Basophil %, basophil (absolute), eosinophil %, eosinophil (absolute), haematocrit, Hb, lymphocyte %, lymphocyte (absolute), MCH, MCHC, MCV, monocyte %, monocyte (absolute), neutrophil %, neutrophil (absolute), platelet, RDW, RBCs, WBCs
- Other:
 - Serum pregnancy test in women of childbearing potential

*Serum potassium will be additionally assessed at time points as noted in the Schedule of Events ([Table 1](#) and [Table 2](#)).

Details on the processing and shipment of specimens are provided in the Laboratory Manual. In the event of an unexplained clinically noteworthy abnormal laboratory test value, the test should be repeated immediately and followed up until it has returned to the normal range and/or an adequate explanation of the abnormality is found.

Details on the clinical laboratories used in this clinical trial, such as address, accreditation certificates, are available in the Trial Master File.

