12.9.6 Clinical Laboratory Tests

For each study period, summaries of actual values and the change from baseline to each time point (when applicable) will be presented for quantitative laboratory parameters.

Laboratory values will be reported in Système International units.

Laboratory test results will be classified according to whether the value was below (L), within (N), or above (H) the laboratory parameter reference range. A summary of treatment-emergent shifts will compare the baseline L/N/H classification for each laboratory test to the L/N/H classification at end of the treatment for each study period. For

serum potassium, shift table comparing the baseline L/N/H classification to each post-baseline L/N/H classification will also be provided.

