4.1.2 Definition of Baseline, Visits and Visit Windows

In general, the baseline is defined as the last available (non-missing) value (scheduled or unscheduled) prior to the first dose in the open-label extension period. For the efficacy endpoints, the 5-D itch scale and the Skindex-10 scale score, analyses will be conducted based on two different baseline definitions. The first definition is that baseline is the last available (non-missing) value (scheduled or unscheduled) prior to the first dose in the open-label extension period. The second definition is that baseline is the last available value (scheduled or unscheduled) before or on the same day as randomisation or if missing as any values during Week 1 (\leq Day 7). As a general rule for safety and efficacy related summaries (e.g., tables), the visit label mentioned in [Table 3](#) will be used to present the corresponding data by study visits for the open-label extension period.

Table 3: Study Visits and Planned Assessment Window for Safety and Efficacy Analysis

Visit	Visit Label	Planned Target Day (Assessment Time Window) for by visit parameters
EoT (Double-blind) / Day 1 (Open-label)	Baseline (Open-label)	Day 1 (\leq Day 1) ^a
Week 2 (Open-label)	Open-label Week 2	Day 8 to Day 14 (Day 8 to Day 21)
Week 4 (Open-label)	Open-label Week 4	Day 22 to Day 28 (Day 22 to Day 35)
Week 6 (Open-label)	Open-label Week 6	Day 36 to Day 42 (Day 36 to Day 49)
Week 8 (Open-label)	Open-label Week 8	Day 50 to Day 56 (Day 50 to Day 63)
Week 10 (Open-label)	Open-label Week 10	Day 64 to Day 70 (Day 64 to Day 77)
Week 12 (Open-label)	Open-label Week 12	Day 78 to Day 84 (Day 78 to Day 91)
EoT/ET (Open-label)	Open-label Week 14	Day 99 (Day 92 to maximum day of [Day EoT/ET visit and Day 99])
	Last Post-baseline (Open-label) ^b	
Follow-up (Open-label)	Follow-up (Open-label) ^c	EoT/ET visit + 7 Days ([EoT/ET visit + 1] to maximum day of [EoT/ET visit + 10, 109])

^a Study Day 1 is defined as the first dose date during the open-label extension period (as per the “Study Drug Administration- Open Label” eCRF page).

^b The last post-baseline visit is defined as the latest value recorded for a given parameter, not including the Follow-up Visit or any visits following the End of Treatment/Early Termination Visit. To be displayed for safety endpoints summary tables.

^c Follow-up (Open-label) is applicable for safety analysis only.

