4.1.3 Planned Assessment Windows

Assessments collected by study week that are collected at early termination visit and unscheduled visits will be assigned to a planned visit window. If the early termination or unscheduled visit day falls into an assessment time window, it will be mapped to the corresponding scheduled analysis visit. Should more than one measurement fall within a visit window, priority is given first to the measurement with a non-missing value in the following order: first, the scheduled assessment; second, an early termination visit; and next, the unscheduled assessment closest to the planned day. In the case that two unscheduled visits are equidistant, the latest will be used. This rule will be applied both to efficacy and safety endpoints. For detailed assessment time window information, please see the above [Table 3](#).

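### The open-label potassium tables do not count, by sequence, the subjects ever high or low after baseline, and an unscheduled high can lose its place to a normal scheduled value in the same window

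*SAP*

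**What the plan says.** SAP 4.1.3 sets the order of preference when several values fall in one window: "first, the scheduled assessment; second, an early termination visit; and next, the unscheduled assessment closest to the planned day". On scope it says "This rule will be applied both to efficacy and safety endpoints", so laboratory data are covered.

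Table 3 in SAP 4.1.2 gives the windows. The Week 4 row reads "Day 22 to Day 28 (Day 22 to Day 35", with the assessment window in the bracket. The windows for Weeks 2 to 12 run without gaps from Day 8 to Day 91, and baseline ends at Day 1. A footnote defines the last value by date: "The last post-baseline visit is defined as the latest value recorded for a given parameter". The follow-up visit and anything after the end-of-treatment or early termination (EoT/ET) visit are left out of it.

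SAP 4.8.2 then defines the shifts. For all tests, "A summary of shifts will compare the baseline L/N/H classification for each laboratory test to the L/N/H classification at end of open-label extension period"; the sentence goes on to add last post-baseline. For potassium: "For serum potassium, shift table comparing the baseline L/N/H classification to each post baseline L/N/H classification (including last post-baseline) will also be provided". Protocol 12.9.6 already planned for potassium a "shift table comparing the baseline L/N/H classification to each post-baseline L/N/H classification", so the SAP follows the protocol and adds the last value.

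The same SAP section lists every laboratory result, unscheduled visits included, and puts all values classed low or high in a separate listing (output 14.3.4.2 for serum chemistry).

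**The concern.** Protocol 7.1 names hyperkalaemia among the common adverse events reported at least 1 percentage point more often than on placebo, and 1.2.2.2 also names it among the serious ones. It is not on the list of adverse events of special interest (protocol 10.8.4.1, SAP 4.8.1), so no special-interest table covers it. Potassium is the one analyte sampled repeatedly in the extension.

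The natural question is how many subjects with normal potassium at open-label baseline went high at any time, in each sequence. No planned laboratory table answers it. Some unscheduled values cannot reach the by-visit or shift tables, and the columns that are planned describe single time points.

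**Working it through.** The plan states no figure here to reproduce. The check has two parts: applying the window rule, and asking what the visit columns can say about ever-high incidence.

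**1. Window rule**

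- Window lengths from Table 3: Week 2 is Days 8–21, Week 4 is 22–35, Week 6 is 36–49, Week 8 is 50–63, Week 10 is 64–77 and Week 12 is 78–91. Each is 14 days (for example 35 − 22 + 1 = 14).
- Days 2 to 7 lie after baseline (up to Day 1) and before Week 2 (from Day 8), so they have no window.
- Example: scheduled potassium normal on Day 24, unscheduled potassium high on Day 31. Both map to Week 4. The scheduled value is kept, so the Day 31 value enters neither the Week 4 summary nor the Week 4 shift. It enters the last post-baseline column only if no later value exists up to EoT/ET.
- Reverse case: protocol 9.4 says that for an unexplained noteworthy abnormal result "the test should be repeated immediately and followed up until it has returned to the normal range" or adequately explained. If the abnormal result was the scheduled draw, the priority rule keeps the high and sets aside the later repeats. The rule hides a high only in the first pattern, or on Days 2 to 7.

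**2. Visit columns against ever-high incidence**

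Inputs: K = 6 scheduled potassium draws (Weeks 2, 4, 6, 8, 10 and 12; protocol Table 2), or K = 7 with the end-of-treatment chemistry panel, which includes potassium. The proportion high at each visit, p, is **assumed**, since the documents give none. It is taken as equal across visits, with every subject having all K values.

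The visit columns fix only p at each visit. The ever-high share then lies between p (the same subjects high every time) and min(1, K × p) (different subjects each time). Under independence it is 1 − (1 − p)^K.

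| Assumed p | K | Lower bound | Independent | Upper bound |
|---|---|---|---|---|
| 5% | 6 | 5% | 1 − 0.95^6 = 26% | 30% |
| 5% | 7 | 5% | 1 − 0.95^7 = 30% | 35% |
| 10% | 6 | 10% | 1 − 0.90^6 = 47% | 60% |
| 10% | 7 | 10% | 1 − 0.90^7 = 52% | 70% |
| 15% | 6 | 15% | 1 − 0.85^6 = 62% | 90% |
| 15% | 7 | 15% | 1 − 0.85^7 = 68% | 100% |

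With positive within-subject correlation the answer falls inside these bounds. Under a latent-normal model with common correlation 0.7 and K = 7, it is 16% at p = 5% and 27% at p = 10%. The visit columns therefore leave ever-high incidence undetermined over a wide range. The end and last columns are single time points too.

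This second part does not measure the effect of the priority rule. That depends on how often an unscheduled high shares a window with a normal scheduled value, for which the documents give no figure.

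**The case against.** The case for leaving the plan alone is substantial.

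- **Listings.** All results are listed, and low and high values have their own listing. A reader might infer that potassium peaks disappear or that subjects ever high cannot be counted. The documents do not support that: the count can be made by hand from output 14.3.4.2, and scheduled highs also appear in the potassium visit shifts and in each visit's maximum (SAP 4.1.1). What is missing is the tabulation.
- **Adverse events.** Protocol 10.5.4 requires reporting when a result comes with symptoms, leads to intervention or moves from normal to pathological, among other criteria. SAP 4.8.1 then counts each subject once per preferred term, by sequence and pooled, outside the windows. This covers much of the ground. It does not fully replace a laboratory count, because 10.5.4 also says that not every out-of-range result qualifies and leaves room for judgement.
- **Direction of protocol 9.4.** A reader might infer that its repeats systematically lead the rule to drop highs. As shown above, where a scheduled draw triggers the repeats, the rule keeps the high.
- **Size.** A reader might take a 5% visit column as understating a 30% incidence. These are different quantities, and the rates are assumed.
- **Exposure and purpose.** A reader might infer that most is lost in the placebo-to-difelikefalin sequence at first exposure, or that two-weekly sampling exists because of hyperkalaemia. No passage or calculation supports the first, and the documents state no reason for the sampling interval.
- **Role of the extension.** Its safety analysis is descriptive, both sequences receive difelikefalin, and the SAP meets protocol 12.9.6. That makes this an improvement to the tables, not a departure from the protocol.

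**Conclusion.** The point holds in a limited form. In the open-label SAP, a high unscheduled potassium that shares a window with a normal scheduled value, or that falls on Days 2 to 7, is absent from the by-visit and shift tables unless it is the subject's last value. Separately, the number of subjects ever high or ever low after baseline is not tabulated by sequence for any laboratory test, and for potassium the planned columns do not determine it. At an assumed 10% high per visit with seven complete samples, it could lie between 10% and 70%. How often the priority rule would displace a high is unknown.

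This is a cheap improvement and concerns potassium. Haematology and the remaining chemistry have one scheduled draw in the extension, at EoT/ET, so on scheduled data the worst value and the end value coincide. Nothing can be concluded about the double-blind tables, because SAP section 1 refers them to a separate SAP that is not among the documents reviewed.

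**What to change.** In SAP 4.8.2, for Table 14.3.5.6, add two shifts by sequence and pooled: baseline class to the class of the highest post-baseline potassium, and baseline class to the class of the lowest. Use all central-laboratory values after the first open-label dose up to the EoT/ET visit, including unscheduled values and those on Days 2 to 7, and state that the 4.1.3 priority rule does not apply to these rows. Leave the existing visit, end and last columns as they are.

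The cost is a few rows in an existing table, with no new data. The downside is that a highest or lowest value becomes more extreme as more samples are drawn, so subjects with more repeats are more likely to shift. Report the number of potassium values per subject by sequence alongside. Potassium measured only in a local laboratory would stay outside these rows, as it is outside the current summaries, and a footnote should say so.

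Equivalent rows for haematology and other chemistry are optional. For the double-blind period, check whether the separate SAP already contains such a row before asking for anything.
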